9.2 SAFETY AND OTHER ASSESSMENTS

Safety in regard to airway trauma induced by tracheal intubation will be assessed by evaluating the short-term effects of the ETT on the airway including subjective and objective measures of laryngeal anatomy and function, in addition to any device-related adverse events. We will record: 1) airway complications at the time of ETT insertion; 2) documentation of a cuff leak prior to study ETT removal; 3) stridor immediately after extubation; 4) requirement for stridor treatment (racemic epinephrine, helium-oxygen gas mixture); or 5) reintubation within 24 hours due to upper airway complications such as stridor or obstruction.

In addition, long-term safety will be assessed by ascertaining the persistence of airway sequelae six months after randomization using a standardized questionnaire via in-person interview (or phone interview). Data collected include complaints of airway symptoms and a speech evaluation.

9.3 ADVERSE EVENTS AND SERIOUS ADVERSE EVENTS

9.3.1 DEFINITION OF ADVERSE EVENTS (AE)

Adverse event means any untoward medical occurrence associated with the use of an intervention in humans, whether or not considered intervention-related (21 CFR 312.32 (a)).

9.3.2 DEFINITION OF SERIOUS ADVERSE EVENTS (SAE)

An adverse event (AE) or suspected adverse reaction is considered "serious" if, in the view of either the investigator, it results in any of the following outcomes: death, a life-threatening adverse event, inpatient hospitalization or prolongation of existing hospitalization, a persistent or significant incapacity or substantial disruption of the ability to conduct normal life functions, or a congenital anomaly/birth defect. Important medical events that may not result in death, be life-threatening, or require hospitalization may be considered serious when, based upon appropriate medical judgment, they may jeopardize the participant and may require medical or surgical intervention to prevent one of the outcomes listed in this definition.

9.3.3.2 RELATIONSHIP TO STUDY INTERVENTION

The causal relationship of an AE to the study protocol will be classified using the following terminology. The given criteria for each term are neither exhaustive nor required to be fulfilled in total for the selection of the respective term:

Relationship to Study Intervention	Unrelated	The AE is clearly not related to the study procedures (i.e., another cause of the event is most plausible and/or a clinically plausible temporal sequence is inconsistent with the onset of the event) or could readily have been produced by a number of other factors.
	Suspected	An AE that follows a reasonable temporal sequence from the initiation of study procedures. Data with sufficient evidence or argument to suggest a causal relationship.
	Certain	The AE is clearly related to the study procedures.

9.3.3.3 EXPECTEDNESS

Expectedness of (serious) adverse events will be assessed by the medical monitor. An unexpected AE is one where the nature or intensity is not consistent with available information. Furthermore, reports that add significant information about the specificity or severity of a known, already documented, adverse reaction constitute unexpected AEs. For example, an AE that is more specific or more severe than expected would be considered “unexpected”.

9.3.4 TIME PERIOD AND FREQUENCY FOR EVENT ASSESSMENT AND FOLLOW-UP

The occurrence of an adverse event (AE) or serious adverse event (SAE) may come to the attention of study personnel during study visits and interviews of a study participant presenting for medical care, or upon review by a study monitor.

All AEs including local and systemic reactions not meeting the criteria for SAEs will be captured on the appropriate eCRF. Information to be collected includes event description, time of onset, clinician’s assessment of severity, relationship to study product (assessed only by those with the training and authority to make a diagnosis), and time of resolution/stabilization of the event. All AEs occurring while on study must be documented appropriately regardless of relationship. All AEs will be followed to adequate resolution.

Any medical condition that is present at the time that the participant is screened will be considered as baseline and not reported as an AE. However, if the study participant’s condition deteriorates at any time during the study, it will be recorded as an AE.

Changes in the severity of an AE will be documented to allow an assessment of the duration of the event at each level of severity to be performed. AEs characterized as intermittent require documentation of onset and duration of each episode.

The study coordinator will record all reportable events with start dates occurring any time after randomization until 7 (for non-serious AEs) or 30 days (for SAEs) after the last day of study participation. Events will be followed for outcome information until resolution or stabilization.

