We do not expect differences in risks at insertion between the PVC-ETT and the EVAC-PU-ETT. However, while the tubes have the same internal diameter, the EVAC-PU-ETT tube has a slightly larger external diameter (due to the additional port) which effectively increase the outer diameter by 0.5 points. This may mean a different tube is requested prior to the intubation attempt or it is requested after a failed attempt is made. If this happens because the outer diameter of the tube is thought to be a problem, a non-study tube will be used. Specifically, if a <7.0 size is needed, then it will not be a study tube since alternative sizes are not available for this study. We will monitor insertion complications, including the need to insert smaller size tubes.

Complications related to mechanical ventilation are not research risks and are instead due to standard of care which subjects would be exposed to outside of the study. However, certain symptoms, like dyspnea, will not be distinguishable between device and ventilator. Assessment of risks will primarily focus on complications to upper airway which are more closely related to the breathing device than the ventilator use. For the trial, we will document whether the symptoms are thought to be related to upper vs lower airway dysfunction (evidence of pulmonary disease or condition), and we will compare the frequency between the two groups.

This study will evaluate cognitive function. We do not expect cognitive changes to represent side effects of the ETT. We hypothesize that decreased cognitive function is a consequence of infection (VAP) as a result of neuroinflammation. We hypothesize that patients that do not experience infection or hypoxemia resulting from pneumonia should have less cognitive dysfunction. If the EVAC-PU-ETT is protective from VAP, then the intervention group should also have less cognitive dysfunction. Therefore, side effects of cognitive dysfunction are not research risks, and are instead risks of the condition they would be exposed to outside of the study.

This study increases the risk of invasion of privacy as patients will be enrolled into this emergency medicine study without his or her consent. We anticipate most subjects will be enrolled in the study under a waiver of consent because this patient population may not immediately have the capacity to provide consent to be in the study.

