7 STUDY INTERVENTION

7.1 STUDY INTERVENTION(S) ADMINISTRATION

7.1.1 SCREENING AND ENROLLMENT

Potential subjects enrolled will be identified through a three-prong process: 1) An automatically generated report listing all new patients admitted to the ICU and receiving mechanical ventilation will be generated daily. All patients listed in the report will be reviewed at the bedside to determine the presence of a study ID bracelet and confirm that a study device was inserted; 2) Self-addressed envelopes for campus mail to the study team provided in the intubation kits and containing the

participant identification information; and 3) Used intubation kits deposited in return bins located in the ED and ICUs will be scanned for tracking and reconciliation of all study devices. In our previous pilot study experience, these strategies allowed 100% success tracking study devices and participants.¹⁰⁶ After identification, study personnel will approach the participant or authorized representative to obtain informed consent for continued study participation.

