9 STUDY ASSESSMENTS AND PROCEDURES

9.1 EFFICACY ASSESSMENTS

The initial study intervention (randomization and placement of a study device [tracheal intubation]) will be performed under exception from informed consent since the event will occur in an emergency situation. At the first available opportunity, an attempt will be made to obtain written informed consent from the participant or the authorized representative to continue participation in the study. Subjects

who have been randomized will be identified within 24 hours of intervention (tracheal intubation), and an attempt to approach the patient or more likely their legally authorized representative will be made immediately upon identification. In some cases, it may be difficult to identify the LAR immediately, but every effort will be made to obtain informed consent within 72 hours of randomization. Throughout the patient's hospitalization, data will be collected continuously from the time of randomization until hospital discharge or death.

A summary of the clinical data variables and definitions are listed below:

Baseline variables

Demographics: Patient demographic characteristics include age in years on the day of hospital admission, gender, race, ethnicity, weight and height, and county/state of residence. Participants' address and contact information will be maintained separately from the case report form and the study datasets, and linked via the study ID number, to enable re-contacting the participants after hospital discharge.

Clinical variables

Intubation procedure: PVC-ETT patients will be treated according to usual care, while EVAC-PU-ETT patients will receive continuous subglottic suctioning until removal of the ETT. As per the manufacturer's recommendation, continuous low-pressure suction at -20 mm Hg will be applied to the suction port. Procedural details of the intubation procedures will be collected as part of standard pre-formed intubation procedure notes. These details include indication for tracheal intubation, ETT type and size, methods of preoxygenation, induction medication, and instruments used. To quantify difficulty with laryngoscopy and ETT insertion, we will record the number of laryngoscopy attempts, and use of gum-elastic bougie to guide insertion of the tube. Furthermore, immediate complications will be gathered including aspiration noted during laryngoscopy, pharyngeal and tracheal injury, and extent of oxygen desaturation.

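### Section 9.3.4 sets the adverse-event baseline at screening but opens the recording window at randomization, so an injury from placing the study tube can be coded either way.

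*Combined protocol and SAP*

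**What the plan says.** Section 9.3.4 contains three rules that bear on the point.

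- The baseline rule: "Any medical condition that is present at the time that the participant is screened will be considered as baseline and not reported as an AE".
- Its exception: if the participant's "condition deteriorates at any time during the study, it will be recorded as an AE".
- The recording window: the coordinator records reportable events with "start dates occurring any time after randomization", up to 7 days (non-serious AEs) or 30 days (SAEs) after participation ends.

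On the order of events, Section 7.1.1 has ventilated ICU patients "reviewed at the bedside to determine the presence of a study ID bracelet and confirm that a study device was inserted". Its other two identification routes, mailed envelopes from the kits and used kits in return bins, also operate after the kit has been used. Section 9.1 adds that subjects "who have been randomized will be identified within 24 hours of intervention (tracheal intubation").

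On insertion harm, Section 3.3.1 says: "We will monitor insertion complications, including the need to insert smaller size tubes". Section 9.3.5 includes tooth trauma, tracheal perforation, esophageal intubation and pneumothorax among the expected AEs.

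**The concern.** A baseline fixed at screening is harmless when screening precedes treatment. Here treatment comes first, so the sentence can absorb harm caused by the intervention into the patient's baseline. Two coordinators could code the same pharyngeal tear differently, and each could cite Section 9.3.4 in support.

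What is at stake is the AE and SAE record. Grading of severity, relationship and expectedness (Section 9.3.3) attaches to AEs. A serious adverse event is defined from an AE or suspected adverse reaction (Section 9.3.2), so a serious insertion injury meets the same ambiguity. The summary promised for each DSMB meeting and for the annual IRB report is a summary of AEs (Section 10.4.4). The trial asks whether the new tube is as safe as the standard one, and most participants are expected to enter without prior consent (Section 3.3.1). The rule for what counts as an AE should therefore have one reading.

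**Working it through.** No sample size, error rate or event count is involved, so the check is one of sequence and cross-reading.

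**Step 1: order of events.**
- Time 0: the kit is opened and the tube placed. Section 9.1 treats randomization and device placement together as the initial intervention, and the Schedule of Activities (Section 2.3) puts randomization assignment in the tube-placement column.
- Time S, after time 0: screening and identification. Prior use of a study kit is an inclusion criterion (Section 6.1). The bedside review is there to "confirm that a study device was inserted". A screen failure is defined as someone who already has a study tube in (Section 6.3). Section 9.1 puts identification no later than 24 hours after time 0.

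**Step 2: apply both rules to an insertion injury starting at time 0.**
- Resolved before S: the baseline sentence does not reach it, and the window does. It is recordable.
- Present at S and later worse: the deterioration exception makes it an AE. It is recordable, though the text does not say whether onset is time 0 or the time of worsening.
- Present at S and not later worse: the window includes it and the baseline sentence excludes it. This is the contradiction.

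Read literally, the baseline sentence leaves a brief injury recordable and removes one that lasts until screening. That cannot be the intention.

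**Step 3: see whether other text settles it.**
- Section 9.3.4 also requires all AEs on study to be documented whatever their relationship, and Section 9.1 requires device-related AEs to be recorded and assessed. Both apply once something counts as an AE, which is what the baseline sentence decides.
- The list in Section 9.3.5 shows that the authors meant to capture insertion injuries as AEs. It reveals intent but does not repeal the baseline sentence.
- The Schedule of Activities starts the device-related AE and SAE rows at ICU Day 1, with no mark under tube placement. This is weak evidence either way, since intubation details are also marked at ICU Day 1.

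**Step 4: see what is captured regardless.** Airway complications during insertion are a listed safety item (Sections 4, 9.2 and 10.4.4). Aspiration, pharyngeal and tracheal injury, and desaturation are gathered with the intubation details (Section 9.1). No section says that these entries are carried to the AE form.

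**The case against.** The strongest reply is that the plan, read as a whole, points toward reporting. The AE definition in Section 9.3.1 has no baseline exception, the window opens at randomization, and insertion injuries are named as expected AEs. This stands, and it defeats a stronger reading that a reader might infer: that insertion injuries are not reportable as adverse events at all. The documents support a contradiction, not an exclusion.

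A reader might also infer that the data are lost, or that the DSMB and the unanticipated-problem route are closed to these events. Neither follows. Insertion complications are collected as safety data in both arms. The unanticipated-problem definition (Section 9.4.1) does not depend on the baseline sentence. The DSMB reviews safety data by arm and defines the data elements it needs (Section 11.1.6).

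Nor do the documents show that the rule is tilted toward the new tube. The sentence applies equally to both arms. Section 3.3.1 expects no difference in insertion risk, although it notes the larger outer diameter of the new tube and promises monitoring.

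Finally, the protocol does not formally define when a participant is screened. The Schedule of Activities places daily screening in the tube-placement column, and Sections 8.1.1 to 8.1.4 describe provider checks before a tube is used. This adds ambiguity. But the scheduled screening looks for patients already ventilated or already given a study tube, and Sections 6.1, 6.3 and 7.1.1 all place the assessment after insertion.

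**Conclusion.** The point holds as an internal contradiction in Section 9.3.4. It is confined to conditions that start between tube placement and screening, are still present at screening and do not later worsen. For those, the literal baseline rule leaves the event out of the AE and SAE record and out of the AE tabulation, while the recording window and the expected-AE list put it in. The consequence is inconsistent coding, grading and tabulation. The six-month laryngeal injury comparison rests on the follow-up assessment and does not depend on this rule.

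The size cannot be given. The documents state no insertion-complication rate, no proportion persisting to screening and no rule for which sentence prevails. Multiplying 1,074 by an assumed rate would also assume that every complication persists, that none worsens and that staff always follow the baseline sentence. The 24 hours is an upper limit on identification, not the delay for every patient.

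The conclusion assumes that screening means the post-intubation identification in Section 7.1.1, which is the reading the eligibility text supports. Severity: should fix.

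**What to change.** Replace the baseline sentence in Section 9.3.4 with a rule to this effect: baseline is the patient's condition immediately before the first intubation attempt with a study kit, and any new or worsened condition from that attempt onward is an adverse event, whether or not it is already present when the patient is identified or enrolled. This aligns the baseline with the section's own window and with the list in Section 9.3.5.

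Add an instruction that insertion complications abstracted from the intubation note that meet the AE definition are entered on the AE form, graded, and included in the tabulation for the DSMB. Mark the tube-placement column for the AE and SAE rows in the Schedule of Activities to match. Section 5.1 says the first 90 participants have completed follow-up, so state whether their insertion events will be re-coded under the same definition.

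The cost is a short protocol amendment and a CRF instruction. Section 9.1 already provides for collecting the source data. The downside is somewhat more AE entries, plus the work of any re-coding.

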9.3.5 ADVERSE EVENT REPORTING

For the duration of patient therapy, the investigators will be responsible for monitoring and recording 1) Unanticipated problems (UPs); 2) Protocol deviations (PDs); 3) Adverse Events (AEs); 4) Serious Adverse Events (SAEs). The following AEs are expected for the study population: abrasion of the arytenoid cartilage vocal process, cartilage necrosis, cicatrix formation, consequences of failure to ventilate including death, damage to the perichondrium, development of dense or diffuse fibrosis invading the entire glottic area, emphysema, endobronchial aspiration, endobronchial intubation (hypoxemia), endotracheobronchial aspiration, epistaxis, esophageal intubation (stomach distension), excoriated membranes of the pharynx, eye trauma, fibrin deposition, formation of subglottic web, fracture-luxation of cervical column (spinal injury), fragmentation of cartilage, glottic edema (supraglottic, subglottic, retroarytenoidal), granuloma of the inner arytenoid area, infections (laryngitis, sinusitis, abscess, respiratory tract infection), inflammation, intermittent aphonia and recurrent sore throat, laryngeal fibrosis, laryngeal granulomas and polyps, laryngeal obstruction, laryngeal stenosis, laryngeal ulcers, laryngotracheal membranes and webs, membranous glottic congestion, membranous tracheobronchitis, mild edema of the epiglottis, mucosal sloughing, paresis of the hypoglossal and/or lingual nerves, perforation of esophagus, perforation of the trachea, pneumothorax, replacement of the tracheal wall with scar tissue, respiratory obstruction, retrobulbar hemorrhage, retropharyngeal abscess, retropharyngeal dissection, rupture of the trachea, sore throat, dysphagia, stricture of nostril, stridor, subglottic annular cicatricial stenosis, submucosal hemorrhage, submucous puncture of the larynx, superficial epithelial abrasion, swallowed tube, synechia of the vocal cords, teeth trauma, tissue burns, tracheal bleeding, tracheal stenosis, trauma to lips, tongue, pharynx, nose, trachea, glottis, palate, tonsil, etc., traumatic lesions of the larynx and trachea, ulcerations exposing cartilaginous rings and minor erosions at cuff site, ulcerations of lips, mouth, pharynx, ulcers of the arytenoid, vocal cord congestion, vocal cord paralysis, vocal cord ulcerations, and death.

All UPs and AEs reported spontaneously by subjects at any point will also be documented. Any medically concerning symptom will be followed until it reaches a satisfactory conclusion, becomes stable, or clinical judgement indicates that further evaluation is not warranted.

9.3.6 SERIOUS ADVERSE EVENT REPORTING

Descriptions of individual serious adverse events (SAEs) and unanticipated problems will be reported as specified in the DMSB charter. The investigators will provide a written notification of reportable events to the DMSB and funding agency in accordance with deferral regulations. All serious adverse events will be followed until resolution or stabilization.

9.3.7 REPORTING OF PREGNANCY

Pregnancy will be determined via screening test provided to all women as part of standard care, so that women who test positive will be excluded. Women will not be excluded based on lactation status.

9.4 UNANTICIPATED PROBLEMS

9.4.1 DEFINITION OF UNANTICIPATED PROBLEMS (UP)

The Office for Human Research Protections (OHRP) considers unanticipated problems involving risks to participants or others to include, in general, any incident, experience, or outcome that meets all of the following criteria:

- Unexpected in terms of nature, severity, or frequency given (a) the research procedures that are described in the protocol-related documents, such as the Institutional Review Board (IRB)-approved research protocol and informed consent document; and (b) the characteristics of the participant population being studied;
- Related or possibly related to participation in the research (“possibly related” means there is a reasonable possibility that the incident, experience, or outcome may have been caused by the procedures involved in the research); and
- Suggests that the research places participants or others at a greater risk of harm (including physical, psychological, economic, or social harm) than was previously known or recognized.

This definition could include an unanticipated adverse device effect, any serious adverse effect on health or safety or any life-threatening problem or death caused by, or associated with, a device, if that effect, problem, or death was not previously identified in nature, severity, or degree of incidence in the investigational plan or application (including a supplementary plan or application), or any other unanticipated serious problem associated with a device that relates to the rights, safety, or welfare of subjects (21 CFR 812.3(s)).

